8.1.5.1.2. Accumulation Ratio

Part 1

Predidicted daily dose accumulation from single dose data (Part 1) for AUC will be as follows:

$$Rp(AUC) = \frac{AUC(0 - \infty)}{AUC(0 - 24)}$$

Point estimates of the mean ratio and associated 90% confidence intervals will be displayed by treatment.

Part 2

Accumulation will also be evaluated for each treatment by determining the ratio of Day 14 (Part 2 cohort 3 and 4) or Day 18 (Part 2 cohort 5) to Day 1 AUC(0- τ) (R(AUC(0- τ)), Cmax (R(Cmax)), and C τ (R(C τ)). Day 1 C τ will be defined as the 24-hr post day 1 dosing concentration (C24 for Day 1). For part 2 cohort 3,4, and 5 the dosing interval is 24-hrs. Therefore, $\tau=24$ hrs.

For Cohort 6 accumulation will be evaluated by determining the ratio of third dose (occurring on Day 15) to first dose (Day 1) for AUC(0- τ) (R(AUC(0- τ)), Cmax

(R(Cmax)), and C τ (R(C τ)). For part 2 cohort 6 the dosing interval is 7 days (168 hrs). Therefore, $\tau=168$ hrs. In Cohort 6, since sampling at 168 hrs post 3rd dose was not collected, it will be predicted using linear model based on the other collected timepoints post dose.

Point estimates of the mean ratios and associated 90% confidence intervals will be displayed by treatment.

Endpoint / Variables

 • Rp(AUC) for Part 1 Where $Rp(AUC) = \frac{AUC(0 - \infty)}{AUC(0 - 24)}$ • R(AUC(0-τ)), R(Cmax), R(Cτ) on Days 1 and 14 for Part 2 Cohort 3 and 4 where, $\tau=24$ hrs • R(AUC(0-τ)), R(Cmax), R(Cτ) on Days 1 and 18 for Part 2 Cohort 5 where, $\tau=24$ hrs • R(AUC(0-τ)), R(Cmax), R(Cτ) on Days 1 and 15 for Part 2 Cohort 6 where, $\tau=168$ hrs 
Where
 $R(Parameter) = \frac{(Parameter\ Value\ on\ Day\ XX)}{(Parameter\ Value\ on\ Day\ 1)}$
Model Specification

 • In Part 1 the mean of the raw mean of the ratio of AUC(0-inf) to AUC(0-24) will be reported. There is no formal modeling. • In the model for Part 2 Cohort 3,4,5,6 the ratio of the specific parameter will be the dependent variable, day will be included as a fixed effect categorical variable with the reference as Day 1, and participant will be included as a random effect.
Model Checking & Diagnostics

 • A compound symmetry covariance structure for the R matrix will be used by specifying "type=CS" on the RANDOM line • In the event that this model fails to converge, alternative correlation structures may be considered such as CSH. • The Kenward and Roger method for approximating the denominator degrees of freedom and correcting for bias in the estimated variance-covariance of the fixed effects will be used. • Normality assumptions underlying the model used for analysis will be examined by obtaining a normal probability plot of the residuals and a plot of the residuals versus the fitted values (i.e. checking the normality assumption and constant variance assumption of the model respectively) to gain confidence that the model assumptions are reasonable. • If there are any departures from the distributional assumptions, alternative models will be explored using appropriate transformed data.

Model Results Presentation

 For Part 1, point estimates of the means of AUC(0-inf) and AUC(0-24), the point estimate of the predicted accumulation ratio, and the associated 90% confidence interval will be presented in tabular format by treatment group. For Part 2, point estimates of the Geometric least squares means and 90% confidence intervals for the accumulation ratio will be presented in tabular format by treatment group.
Subgroup Analyses

 Not Applicable.
Sensitivity and Supportive Analyses

 Not Applicable.

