Vital signs		X	X	X (Days 2, 4, and 6)	X	X (Days 10, 12 and 14)	X	X		X		X		Vital signs to be performed pre-dose. Temperature will be monitored every day during study participation. For further detail, see Section 8.1.2
12-lead safety ECGs		X	X	X	X	X	X	X	X	X	X	X		ECG should be performed pre-dose on dosing days. ECG timepoints may be reduced in subsequent dosing groups. For further detail, see Section 8.1.4
Testing for SARS CoV-2	X			X (Day 7)		X (Day 14)						X		An additional SARS-CoV-2 test will be performed approximately one week prior to admission to the unit. Weekly SARS-CoV-2 testing is required while in the unit (Days 7, 14) and on discharge (Day 20). An approved molecular

Procedure	Pre-Treatment Days		Week 1		Week 2		Week 3		In House Post Treatment Days					Notes
	Treatment Days		Treatment Days		Treatment Days									
	-2	-1	1	2, 3, 4, 5, 6, 7	8	9, 10, 11, 12, 13, 14	15	16 24h	17 48h	18 72h	19 96h	20 120h		
														Hours (h) relate to PK sampling post last dose
Drug/alcohol/nicotine screen	X													test (PCR) will be used. For further detail see Appendix 7 and Section 8.1.3
Haematology/Chemistry/Urine tests		X	X	X (Days 2, 4 and 6)	X	X (Days 9, 11 and 13)	X		X		X	X		For further detail, see Appendix 2
Pregnancy Test	X													Female participants only. For further detail see Appendix 2
VH3739937 Dose Administration			X		X		X							Weekly oral dose on Days 1, 8 and 15. Randomization to occur on Day 1 prior to dosing. For meal instructions prior to dose, see Section 5.3.1
Meals	Per site usual practice													
Plasma PK Sampling			X	X	X	X	X	X	X	X	X	X		2mL of blood will be collected at pre-dose (within 15 mins prior to dosing) and 1, 2, 3, 4, 5, 6, 7, 8, 9, 10, 12, and 16 h on Days 1, 8 and Day 15. The 24 h post day 1 dose collection on Days 2, 9 and 15 will be taken at post-dose collection timepoint. At all other timepoints on non-dosing days (Days 3, 4, 5, 6, 7, 10, 11, 12, 13, 14, 16, 17, 18, 19, 20), samples will be drawn at the post-dose

Procedure	Pre-Treatment Days		Week 1		Week 2		Week 3		In House Post Treatment Days					Notes		
	Treatment Days		Treatment Days		Treatment Days											
	-2	-1	1	2, 3, 4, 5, 6, 7	8	9, 10, 11, 12, 13, 14	15	16 24h	17 48h	18 72h	19 96h	20 120h				
Urine PK			X	X (Day 2, end of 24hr collection from Day 1)	X	X (Day 9, end of 24hr collection from Day 8)	X	X (Day 16, end of 24hr collection from Day 15)						Hours (h) relate to PK sampling post last dose		

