All participants will have a screening visit within 28 days prior to first dose and a follow-up visit approximately 28 days after the last dose. All dosing will be conducted in a hospital based inpatient clinical trial unit. Study participants will be confined to the clinic from Day -2 until discharge. Additional outpatient visits will be required for all study parts. Flexibility of visit scheduling may be required if a pandemic situation applies (see Appendix 7). Otherwise, study assessments will be performed as indicated in the SoA presented in this protocol.

A summary of the overall study design, including proposed doses, sample size, and order, is presented in Figure 3 and Figure 4 below.

Figure 3 Phase 1 Study in Healthy Participants using planned doses of VH3739937 Part 1 and Part 2

A=Active; P=Placebo

QD = once daily; QW = once weekly

*= Period 4 may include participants from both Cohorts 1 and 2

Highlighted cohorts and treatment periods denotes completed

The doses shown in [Figure 3](#) above are intended to demonstrate general concepts relating to factors of escalation. The modelling and simulation implemented using the data currently available following oral administration of a suspension formulation in the fed state indicated the predicted efficacious dose for the daily dose is 25 mg and the weekly dose is 500 mg. Due to the observed half-life of ~90 h, the anticipated accumulation ratio following repeated daily and weekly doses is ~6-fold and 1.3-fold, respectively. Dosing will be conducted in accordance with safety and PK stopping criteria (Section [7.1.4](#)).

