8.1.1.2. Derived Pharmacokinetic Parameters

Pharmacokinetic parameters will be calculated by standard non-compartmental analysis according to current working practices and using the currently supported version of WinNonlin. All calculations of non-compartmental parameters will be based on actual sampling times. Pharmacokinetic parameters listed will be determined from the plasma concentration-time data, as data permits.

Parameter	Parameter Description
AUC(0-inf)	Area under the concentration-time curve extrapolated to infinity will be calculated as: AUC = AUC(0-t) + C(t) / lambda_z
AUC(0-t)	Area under the concentration-time curve from time zero to the time of the last quantifiable concentration (C(t)) will be calculated using the linear trapezoidal rule for each incremental trapezoid and the log trapezoidal rule for each decremental trapezoid.
AUC(0-24)	Area under the plasma concentration time curve from zero to 24 hrs
AUC(0-168)	Area under the plasma concentration time curve from zero to 168 hrs
AUC(0- τ)	Area under the curve (Area under the plasma drug concentration-time curve from pre-dose to the end of the dosing interval at steady state)
%AUCex	The percentage of AUC (0-inf) obtained by extrapolation (%AUCex) will be calculated as: [AUC(0-inf) – AUC(0-t)] / AUC(0-inf) x 100
C _{max}	Maximum observed concentration, determined directly from the concentration-time data.
C ₂₄	Concentration at 24 hours post-dose
C ₁₆₈	Concentration at 168 hours post-dose
C _{last}	Last quantifiable concentration

Parameter	Parameter Description
$C\tau$	Pre-dose (trough) concentration at the end of the dosing interval
t_{max}	Time to reach C_{max} , determined directly from the concentration-time data.
$t_{1/2}$	Apparent terminal half-life will be calculated as: $t_{1/2} = \ln 2 / \lambda_{z}$
t_{lag}	Absorption lag time
t_{last}	Time of last quantifiable concentration
CL/F	Apparent oral clearance

NOTES:

- Additional parameters may be included as required.

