8.1.4. Strategy for Intercurrent (Post-Randomization) Events

Missing data will not be imputed, regardless of the reason.

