13.10.6. Pharmacokinetic Tables

Pharmacokinetic: Tables					
No.	Population	GSK Standard / Example Shell	Title	Programming Notes	Deliverable [Priority]
PK Concentration					
4.1.	PK	PK01	Summary of VH3739937 Plasma Pharmacokinetic Concentration (ng/mL) -Time Data by Treatment	Page by part	SAC [1]
4.2.	PK	PK03	Summary of Derived VH3739937 Plasma Pharmacokinetic Parameters by Treatment		SAC [1],HL
4.3.	PK	PK05	Summary of Log-Transformed Derived VH3739937 Plasma PK Parameters by Treatment		SAC [1],HL
Dose Proportionality, Accumulation, and Steady State					
4.4.	PK	PK_T1	Summary Results of Single Dose Proportionality Assessment Using Power Model – Part 1	Stats output, Non-Standard Shell PK_T1 PK parameters: AUC(0-inf), AUC(0-t), Cmax	SAC
4.5.	PK	PK_T1	Summary Results of Multiple Dose Proportionality Assessment Using Power Model – Part 2	Stats output Non-standard shell PK_T1 PK parameters: AUC(0-inf), AUC(0- τ), Cmax	SAC
4.6.	PK	PK_T2	Summary Results of Steady State VH3739937 Concentrations Assessment – Part 2	Stats output Non-standard shell PK_T2 Use up to day 14 for cohort 3 and 4 and day 18 for cohort 5.	SAC

Pharmacokinetic: Tables					
No.	Population	GSK Standard / Example Shell	Title	Programming Notes	Deliverable [Priority]
				Add footnote: Ctrough was collected on days 2,3,4,6,8, 10,11,12,13,14,15 for cohort 3 and 4 and days 2,3,4,6,8, 10,11,12,13,14,15, 16, 17,18 for cohort 5. Use C_{τ} to determine steady state for daily dosing MAD. See example from Table 4.13 from study 207187	
4.7.	PK	PK_T3	Summary Results of VH3739937 PK Parameter Treatment Comparisons Predicted Accumulation Ratio- Part 1	Stats output, Non-Standard Shell at end of RAP Non-standard shell PK_T3	SAC
4.8.	PK	PK_T4	Summary Results of VH3739937 PK Parameter Treatment Comparisons Accumulation Ratio- Part 2	Stats output, Non-standard shell PK_T4 Add footnote: In Cohort 6, since sampling at 168 hrs (7 days) post 3 rd dose was not collected, it will be approximated by 192 hrs post dose.	SAC
Relative Bioavailability/Food Effect					
4.9.	PK	PK_T5	Summary of Result of Plasma VH3739937 Pharmacokinetic Parameter Treatment Comparisons for Relative Bioavailability	Stats output	SAC [1], HL

Pharmacokinetic: Tables					
No.	Population	GSK Standard / Example Shell	Title	Programming Notes	Deliverable [Priority]
				PK Parameters: $AUC_{(0-24)}$, $AUC_{(0-\infty)}$, and C_{max} Ratio: Test/Reference (Tablet/PiB) See study mid208131 Table 4.4 for reference Non-standard shell PK_T5	

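### Cohort 6 accumulation: the SAP gives two incompatible rules for the unsampled 168-h value after dose 3, and the Table 4.8 footnote rule understates R(Cτ) by about 17%

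*SAP*

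**What the plan says.** SAP 8.1.5.1.2 defines Cohort 6 accumulation as the third dose (Day 15) over the first dose (Day 1) for AUC(0-τ), Cmax and Cτ, with τ = 168 h. For the missing value it states: "since sampling at 168 hrs post 3rd dose was not collected, it will be predicted using linear model based on the other collected" post-dose time points. It does not say whether the line is fitted to raw or log concentration, or to which samples.

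The programming note for Table 4.8 in SAP 13.10.6 orders a footnote under which, for the same value, "it will be approximated by 192 hrs post dose". Neither place refers to the other or sets a precedence.

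The sampling gap is real. Protocol Table 5 takes serial samples up to "12, and 16 h on Days 1, 8 and Day 15", then daily in-unit samples to Day 20 (120 h after dose 3). The next sample is the outpatient visit on Day 23 (192 h). After doses 1 and 2, by contrast, the 168-h value is observed, as the pre-dose sample on Days 8 and 15.

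Protocol 4.1 gives a half-life of about 90 h and says "the anticipated accumulation ratio following repeated daily and weekly doses is ~6-fold and 1.3-fold, respectively".

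**The concern.** Concentration is falling between 168 h and 192 h, so a 192-h value used as a 168-h trough is always too low. The Day 1 value it is divided by, if C168, is taken at the correct time, so the error does not cancel. The text rule has its own weakness: a straight line through an exponential decline is wrong on the raw scale, and the error grows as earlier samples are added.

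The Cohort 6 R(Cτ) in Table 4.8 therefore depends on which SAP sentence the programmer follows and, under the text rule, on choices the SAP leaves open. Accumulation is a named secondary objective, and Cohort 6 is the only weekly-dosing cohort.

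**Working it through.** **Inputs.** Half-life h ≈ 90 h (Protocol 4.1); linear one-compartment model with first-order absorption (Protocol 2.2.1); τ = 168 h and dose 3 over dose 1 (SAP 8.1.5.1.2); samples at 120, 192, 264 and 360 h after dose 3 (Protocol Table 5). Assumed here: half-life range 70 to 110 h, and absorption rate ka of 0.2 to 1.0 per h.

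**The protocol's own figures.** At steady state R = 1/(1 − 2^(−τ/h)). Daily: 1/(1 − 0.831) = 5.93, against about 6 stated. Weekly after three doses: 1 + 2^(−168/90) + 2^(−336/90) = 1 + 0.274 + 0.075 = 1.349, which rounds to the stated 1.3. (Weekly steady state is 1.378.) The 500 mg weekly medians in Protocol Table 11 (Cmax 1.5, Cτ 0.429 µg/mL) imply a half-life of 87 to 91 h for an assumed tmax of 3 to 10 h. The inputs are consistent.

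**Footnote rule, R(Cτ).** C192/C168 = 2^(−24/h).

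| Half-life | True R(Cτ) | C192/C168 | R(Cτ) under footnote | Error |
|---|---|---|---|---|
| 70 h | 1.225 | 0.788 | 0.966 | −21% |
| 90 h | 1.349 | 0.831 | 1.122 | −17% |
| 110 h | 1.467 | 0.860 | 1.261 | −14% |

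At 90 h the result does not change over the assumed ka range.

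**Text rule, 90 h.** A line through 120 h and 192 h is read at 168 h. Per unit of a decay curve starting at 1, C120 = 0.397 and C192 = 0.228. Raw-scale interpolation gives 0.397 − (0.397 − 0.228) × 48/72 = 0.284, against a true 0.274: +3.7%. On log concentration the same interpolation is exact. With other sample sets:

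| Samples in the line | Raw scale: R(Cτ), error | Log scale: error |
|---|---|---|
| 120, 192 h | 1.40, +3.7% | 0% |
| 120 to 264 h | 1.46, +8% | 0% |
| 72 to 360 h | 1.67, +24% | 0% |
| All from 1 h (ka 0.2 to 1.0) | 1.84 to 2.06, +36% to +53% | −6.6% to −0.8% |

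**R(AUC(0-τ)), 90 h**, using the SAP's linear-up, log-down rule on scheduled times. If C192 is placed at 168 h, the ratio falls by about 1.4%. If AUC(0-192) stands in for AUC(0-168), it rises by 6.4% to 6.6%. At ka 0.3 the true 1.362 becomes 1.343 or 1.452. Log-linear interpolation gives no error. R(Cmax) does not use the value.

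**Day 1 denominator.** Protocol 9.4.4 lists Cohort 6 among the accumulation ratios and then takes C24 on Day 1 as that day's Cτ, with no exception for weekly dosing. SAP 8.1.5.1.2 gives the C24 definition only in its daily-cohort paragraph and gives none for Cohort 6. SAP 8.1.2 derives Day 1 C168, which fits τ = 168 h. With C24 as denominator, R(Cτ) would be about 0.45 at 90 h.

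**The case against.** The best defence is that the effect is small in consequence. The ratios are descriptive, rest on 7 active participants and do not drive escalation. The footnote would also print under Table 4.8, so the substitution would be disclosed. That is fair and limits the weight of the point, but disclosure does not remove the bias or settle which rule applies.

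A second defence is that the text rule already intends a model-based prediction, so deleting the footnote would be enough. It would not: taken literally on the raw scale with every sample, the text rule errs further than the footnote, in the opposite direction.

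Third, "Missing data will not be imputed, regardless of the reason" (SAP 8.1.4) might seem to bar any derived value. It is weak support either way. The 168-h sample was never scheduled, SAP 8.1.5.1.2 itself prescribes a prediction, and SAP 13.5.3 refers concentration imputation to an internal guide not available here.

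Two stronger readings are not supported.

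- A reader might infer that the report would show accumulation reversing, because the true dose-2 ratio at 90 h is 1.27 and the footnote's dose-3 value is 1.12. The SAP summarises Day 8 C168 but plans no dose-2 ratio; a reader would have to construct it.
- A reader might infer that the Part 2 model gives invalid intervals. In it, "the ratio of the specific parameter will be the dependent variable, day will be included as a fixed effect categorical variable", with Day 1 as reference. With one ratio per participant, the least squares mean and its standard error are correct and the day term is redundant. Too narrow an interval (simulated coverage of 74% to 79% for a nominal 90%, n = 7, assumed ratio CV 15% to 25%) arises only if constant Day 1 ratios of 1 are entered and the later day's mean is reported instead of the contrast. Nothing in the SAP says that this will be done, and its promise of "point estimates of the Geometric least squares means and 90% confidence intervals for the accumulation ratio" already points to a log analysis. This is a wording matter.

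**Conclusion.** The SAP contains two incompatible rules for one reported quantity. At the documents' half-life the footnote rule is 17% low for R(Cτ). That figure is measured against the true 168-h value, not against the text rule, whose result cannot be fixed until its scale and samples are stated. The direction holds at any half-life; the size rests on mono-exponential decline and ranges from 21% to 14% over the assumed 70 to 110 h. The text rule is safe only on log concentration with post-absorption samples. R(AUC(0-τ)) is affected slightly and R(Cmax) not at all. The Cohort 6 Day 1 denominator also needs stating. The SAP should be corrected before Table 4.8 is programmed; nothing here bears on dosing or on the primary endpoints.

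**What to change.** Put one rule in both SAP 8.1.5.1.2 and the Table 4.8 footnote:

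> The dose-3 168-h concentration in Cohort 6 will be derived per participant by log-linear interpolation between the 120-h and 192-h concentrations at actual times (or from the log-linear terminal slope if one of these is missing), and used as Cτ and as the end point of AUC(0-168). The Day 1 denominator for Cohort 6 R(Cτ) is C168, not C24.

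This agrees with SAP 8.1.1.2, which already applies "the log trapezoidal rule for each decremental trapezoid". The terminal-slope fallback avoids losing a participant from a group of 7. SAP 2.1, which records no departures from the protocol's analyses, is the place to note the clarification of Protocol 9.4.4.

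As a minor clarification covering Cohorts 3 to 6, state that the Part 2 model takes the log-transformed parameter as response, with day fixed and participant random. It should report the exponentiated contrast of the final dosing day (Day 14, 15 or 18) minus Day 1, with its 90% CI.

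Cost: SAP wording, one footnote and the matching program code. No new samples and no change to the trial's design.

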To characterize the population pharmacokinetics of VH3739937 and identify important determinants of variability, a population model was conducted as an alternate analysis approach to characterize the pharmacokinetics and the simulation was implemented to predicted the higher single dose and multiple dose cohort PK profile based on the model. The PK of VH3739937 following oral administration was adequately characterized by a linear one-compartment model with first-order absorption and first-order elimination, and with a dose factor and inter-individual variability on CL/F and on the magnitude of proportional residual error. The simulations for higher single dose 640 and 800 mg, multiple daily dose 50 and 100 mg and the multiple weekly dose 500 mg were conducted to predict the PK profile to obtain the Cmax and AUC for safety cover. More detailed information can be found in the Investigator's Brochure Supplement [GlaxoSmithKline Document Number [2021 RPS_CLIN_004025](#)].

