
 To predict the accumulation from single dose data (Part 1) and assess accumulation of VH3739937 after repeat doses (Part 2 at steady state) 	
Accumulation indices for PK parameters for VH3739937:
 
 Part 2 (repeated dose): Observed accumulation ratios: $RAUC_{(0-\tau)}$, $R(C_{max})$, $R(C_{\tau})$

 To assess time to steady-state of VH3739937 (Part 2) 	
Derived PK parameters for VH3739937:
 
 Part 2 (repeated dose): 
 Cohorts 3 and 4: Pre-dose concentrations on Day 2-14 Cohort 5: Pre-dose concentrations on Day 2-18
Exploratory	

 To assess the exposure response relationship between VH3739937 and safety parameter, including QTcF following single and repeated administration (Part 1 & 2) 	
 Change-from-baseline QTcF ($\Delta QTcF$)

Objectives	Endpoints
• To collect plasma and urine samples for analysis of metabolites of VH3739937	• Metabolites of VH3739937 in plasma and urine. The analyses will be conducted and reported separately from this protocol.
• To characterize renal excretion of VH3739937, as data permits	• Urinary recovery of VH3739937 ($Ae[0-x]$), $Ae[0-\tau]$ and $Ae[0-t]$) and renal clearance (CLR)
• To collect duodenal bile for analysis of metabolites of VH3739937 (Part 2, Cohort 5 only)	• Metabolites of VH3739937 in duodenal bile. The analyses will be conducted and reported separately from this protocol

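### Predicted accumulation is the infinite-dosing limit, while the paired observed accumulation is taken after 14 or 18 doses and averaged on a different scale; under linear PK, timing alone puts observed about 7.5% (Day 14) or 3.6% (Day 18) below predicted

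*SAP*

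**What the plan says.** The secondary objective in Protocol 3, repeated in SAP 2.2, is to predict accumulation from Part 1 and to "assess accumulation of VH3739937 after repeat doses (Part 2 at steady state").

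**Prediction (Part 1).** SAP 8.1.5.1.2 introduces the formula with "daily dose accumulation from single dose data (Part 1) for AUC will be as follows" and defines Rp = AUC(0-inf)/AUC(0-24). SAP 13.5.3 and 13.6.4 repeat it. On averaging, the section says "In Part 1 the mean of the raw mean of the ratio of AUC(0-inf) to AUC(0-24) will be reported" and adds that nothing is formally modelled.

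**Observation (Part 2).** For the daily cohorts the SAP takes "the ratio of Day 14 (Part 2 cohort 3 and 4) or Day 18 (Part 2 cohort 5) to Day 1", with a 24 h interval. For Cohort 6 it takes the third dose over the first, with a 168 h interval. The Part 2 results are to be "point estimates of the Geometric least squares means and 90% confidence intervals for the accumulation ratio". The model specification, however, makes the untransformed ratio the dependent variable.

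The two sets of results appear in consecutive tables, 4.7 and 4.8 (SAP 13.10.6).

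**The concern.** Under linear PK, AUC(0-inf)/AUC(0-24) is the accumulation ratio once dosing has gone on indefinitely. Fourteen daily doses span 336/90 = 3.7 half-lives and eighteen span 432/90 = 4.8, so neither reaches that limit. A second difference points the same way: an arithmetic mean of ratios in Part 1 exceeds a geometric mean of the same ratios.

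The natural use of a predicted and an observed ratio under one objective is to ask whether single-dose PK forecasts repeat dosing. As defined, the expected answer under exact linearity is that observed accumulation falls short. A reader who takes the steady-state label at face value could attribute that shortfall to the drug, for example to clearance changing over time, when it comes from the definitions.

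**Working it through.** **Inputs.** Half-life: "Due to the observed half-life of ~90 h" (Protocol 4.1). PK model: "adequately characterized by a linear one-compartment model with first-order absorption and first-order elimination" (Protocol 2.2.1). Dosing interval 24 h; Day 14 for Cohorts 3 and 4, Day 18 for Cohort 5 (SAP 8.1.5.1.2).

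**1. Reproduce the plan's figure.** The protocol states "the anticipated accumulation ratio following repeated daily and weekly doses is ~6-fold and 1.3-fold, respectively". With k = ln2/90, the infinite-dosing daily ratio is 1/(1 − exp(−24k)) = 5.93, which agrees with about 6. The weekly ratio is 1/(1 − exp(−168k)) = 1.38 at the limit and 1.35 after the third dose, close to the stated 1.3.

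**2. Timing.** By superposition, the AUC over the interval after dose n equals the single-dose AUC(0-24n). The observed ratio is therefore 5.93 × (1 − exp(−24kn)).

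| | Ratio | Below the limit |
|---|---|---|
| Infinite dosing (Rp) | 5.93 | – |
| Day 14 (n = 14) | 5.48 | 7.5% |
| Day 18 (n = 18) | 5.71 | 3.6% |

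For half-lives of 80 to 100 h, the Day 14 gap runs from 5.4% to 9.7% and the Day 18 gap from 2.4% to 5.0%. First-order absorption at an assumed 0.3/h raises Rp itself to 6.81 but leaves the gaps at 7.7% and 3.7%.

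**3. Type of mean.** For a lognormal ratio, geometric/arithmetic = 1/√(1 + CV²). Neither document gives a CV for the accumulation ratio; the 25%, 35% and 50% in Protocol 9.5 are for AUC. The range below is an assumption. It also takes Part 1 as the arithmetic mean of individual ratios and Part 2 as geometric. Combined gap = 1 − (timing fraction) × (geometric/arithmetic):

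| Assumed ratio CV | Geometric/arithmetic | Day 14 | Day 18 |
|---|---|---|---|
| 20% | 0.981 | 9.3% | 5.5% |
| 25% | 0.970 | 10.3% | 6.5% |
| 30% | 0.958 | 11.4% | 7.7% |

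A simulation of 400,000 one-compartment subjects, with the same CVs placed on the elimination rate, gives 9.7%, 10.8% and 12.2% at Day 14 and 5.7%, 6.8% and 8.2% at Day 18.

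**4. Size against noise.** Each dose has 6 active participants in Part 1 and 7 in Part 2. At an assumed ratio CV of 25%, the log-scale SD is √ln(1.0625) = 0.246. The SE of the difference in mean log ratio is 0.246 × √(1/6 + 1/7) = 0.14. The offset at the same CV is −ln(1 − 0.103) = 0.11, less than one SE.

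**The case against.** The strongest reply is that the plan never compares the two ratios. They are separate endpoints in separate tables, and neither document specifies an observed-to-predicted ratio, a test or a decision rule. No dose is common to Parts 1 and 2, and the population PK model includes a dose factor, so no row of Table 4.7 matches a row of Table 4.8 exactly. AUC(0-inf)/AUC(0-24) is a correct steady-state prediction and agrees with Protocol 9.4.4. The trough-slope analysis in SAP 8.1.5.1.3 examines separately whether steady state was reached. For a single cohort the offset is lost in the noise.

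Most of this stands, and it limits the point to interpretation. It does not remove the mismatch: one objective joins the two quantities, the offset has a known direction in Cohorts 3, 4 and 5 alike, and the trough-slope analysis does not adjust the ratio.

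The averaging part is less secure. The Part 1 sentence could mean a mean of ratios or a ratio of means. If the Part 2 model were run on the untransformed ratio as written, the extra few percent would disappear. The timing gap would not.

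A reader might also infer that Day 14 CL/F is overstated by about 8% (1/0.925 = 1.08). The documents do not support that: SAP 8.1.1.2 names CL/F as apparent oral clearance and gives no formula.

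**Conclusion.** The point holds as a mismatch of definitions with modest, one-directional consequences. The firm figures are about 7.5% at Day 14 and 3.6% at Day 18. They rest only on the protocol's approximate half-life and linear PK. The larger figures, about 9-11% and 5.5-8%, also need an assumed ratio CV of 20-30% and the arithmetic-versus-geometric reading.

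A reader might infer a fixed shortfall of around 10% in every cohort. The documents do not support this, because they give no CV for the ratio and Cohort 5 is assessed at Day 18, where the timing gap is about half as large. A reader might also infer that the trial would wrongly conclude that clearance is time-dependent. No such analysis is planned; the risk is only in how Tables 4.7 and 4.8 are read side by side.

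Cohort 6 is a related gap. The SAP's prediction uses 24 h only, so the weekly ratio has no matching prediction. The change is worth making before reporting.

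**What to change.** In SAP 8.1.5.1.2, with matching edits in 8.1.1.2, 13.5.3 and 13.6.4:

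- Keep AUC(0-inf)/AUC(0-24), labelled as the steady-state prediction.
- Add AUC(0-336)/AUC(0-24) to set beside Day 14 and AUC(0-432)/AUC(0-24) to set beside Day 18. Under linear PK the expected gap is then zero.
- Analyse log ratios in both parts and report geometric means with 90% CIs. In Part 2, model the log parameter with day as a fixed effect and participant as random, and back-transform the Day 14 (or Day 18) minus Day 1 difference. This also resolves the conflict between an untransformed dependent variable and geometric least squares means.
- In the objective and in Table 4.8, describe the daily ratios as after 14 doses or after 18 doses, not as steady state.

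**Cost.** No new data; a few partial AUCs, some partly extrapolated. The 192 to 360 h visits came with Amendment 2, after the 10-640 mg single-dose data had been acquired, so coverage to 336 h cannot be confirmed for those doses. If sampling stopped at 120 h, the extrapolated share at a 90 h half-life would be 2^(−120/90) = 40% of AUC(0-inf). For AUC(0-336) it would be (0.397 − 0.075)/(1 − 0.075) = 35%. With sampling to 360 h, AUC(0-432) needs (0.0625 − 0.0359)/(1 − 0.0359) = 2.8%, against 6.3% for AUC(0-inf). In each case the added ratio extrapolates less than the one already planned.
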